For Aim 3, an improved survival of Arrowg+ard Blue Advanced midline catheters will be evaluated by functionality of catheter for intravenous therapy prior to patient discharge. The event is failure of functionality identified during follow-up assessment during hospitalization. Duration of dwell and functional failure of the catheter will be employed to estimate catheter survival.

Study Design

We propose a prospective single-site, parallel, two-arm, randomized investigation to assess catheter-related symptomatic UEVT, catheter-related bloodstream infection, and functionality of two single lumen midline catheters: AngioDynamics BioFlo 4 F and Teleflex Arrowg+ard Blue Advance 4.5 F. The research protocol was approved by the Institutional Review Board of Beaumont Research Institute. Written informed consent will be obtained from all participants.

All inpatients 18 years of age and older that require midline catheter placement by the bedside vascular access team will be eligible participants. Patients will be excluded if: Do not meet inclusion criteria 2. Multiple lumens required 3. Alternative diameter of catheter used 4. If already enrolled once prior 5. Withdraw voluntarily from the study 6. Are receiving oral, intravenous, or subcutaneous treatment dose anticoagulation (prophylaxis with anticoagulant is permissible).

Research staff of Beaumont Health Institute will allocate two midline catheters to eligible participants according to a pre-generated randomized list at a 1:1 ratio in block randomization to AngioDynamics BioFlo or Teleflex Arrowg+ard Blue Advanced midline catheters. Participant enrollment will take place from November 2018 until patient recruitment is complete. Demographic and health-related information will be obtained from electronic medical records during enrolled period at William Beaumont Hospital.

Practitioner Participation/Training

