Advanced Practice Providers within the bedside PICC/Midline service at the Royal Oak campus are eligible to place catheters for this study. A cohort of fifteen providers are possible volunteers to be trained to place catheters for this study. Placing catheters for this study is not required and will be carried out on a strictly voluntary basis. All advanced practice providers are credentialed in placing PICCs and midlines by institutional policy and have greater than one year of experience in these procedures. None of the providers have previous experience with the Teleflex Arrowg+ard Blue Advance midline catheter. The clinical team from Teleflex will be expected to develop an educational/training pathway for providers to achieve proficiency prior to subject recruitment. A possible training/credentialing pathway may consist of: 1 hour didactic training followed by phantom training on a vein block and required successful placement of 2-4 catheters on real patients.

Initial Assessment

After written informed consent is obtained, investigators will carry out additional evaluation at the bedside. The research team will capture and save images of vessel depth and vessel diameter in short axis using the Sonosite S1 ultrasound equipment. Ultrasound guidance will be used for the initial assessment and procedure. The high frequency linear array transducer will be used for all procedures. Inserters will evaluate the vessel for valves, thrombosis, trajectory, and collapsibility per routine care. If the vein is appropriate for cannulation, the practitioner will continue with the procedure. Post-cannulation and post securement, functionality is confirmed with blood sampling (10 cc) and flush without resistance.

The research team also will document practitioner details, the vascular access device (VAD) used, the time of VAD placement, number of attempts, need for a rescue inserter, the vein that was cannulated, depth and diameter of the vein, and the indication for VAD placement. An attempt is defined as each time the needle punctures the skin. Data will be collected from the electronic medical record and includes: age, gender, BMI, vital signs, relevant past medical history. Specific medical history of interest includes: 1. VTE 2. Cancer (within past 6 months) 3. Hypercoaguable state 4. Current pregnancy/up to 8 weeks postpartum 5. Major surgery/major trauma within past 4 weeks 6. Estrogen supplementation 7. Long

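### The inserter's vein judgement is not placed before the catheter allocation is revealed, so non-insertion or device switching could differ by arm

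*Combined protocol and SAP*

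**What the plan says.** Under Study Design, entry is broad: "All inpatients 18 years of age and older that require midline catheter placement by the bedside vascular access team will be eligible participants". None of the listed criteria concerns the vein. One exclusion reads "Alternative diameter of catheter used", which turns on the catheter actually placed.

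The same section says that research staff "will allocate two midline catheters to eligible participants according to a pre-generated randomized list at a 1:1 ratio in block randomization". The devices are "two single lumen midline catheters: AngioDynamics BioFlo 4 F and Teleflex Arrowg+ard Blue Advance 4.5 F". Block size, concealment and the moment at which the inserter learns the allocation are not given.

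The Initial Assessment section begins: "After written informed consent is obtained, investigators will carry out additional evaluation at the bedside". It continues: "The research team will capture and save images of vessel depth and vessel diameter in short axis". The inserter then looks at collapsibility, trajectory, valves and any thrombus as in routine care, with no numerical threshold. The step ends: "If the vein is appropriate for cannulation, the practitioner will continue with the procedure". Nothing is said about a participant whose vein is not judged appropriate. The vein used, with its depth and diameter, is recorded.

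The Practitioner Participation/Training section states that no provider has used the Teleflex midline before. The Statistical Analysis text adjusts for participant characteristics, which it does not list, and names no analysis population.

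**The concern.** Randomisation protects the comparison only if decisions about who stays in the trial cannot depend on the assigned arm. Here a decision that determines whether the patient receives the catheter at all rests with the inserter, and the plan does not put it ahead of the allocation. There are two reasons why the decision could differ by arm: catheter size, and unfamiliarity with one of the devices.

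At stake are Aim 1 (thrombosis) and Aim 3 (catheter survival). A patient who never receives the study catheter cannot have a thrombosis caused by it and has no dwell time. Dropping such patients from one arm breaks the balance of the groups. Keeping them as event-free lowers that arm's rate by absence of exposure. If the losses fall on poor veins in the Teleflex arm, and poor veins clot more often, the error favours Teleflex, which is the direction the one-sided design is looking for.

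**Working it through.** **1. Order of steps.** Study Design allocates to eligible participants. Initial Assessment starts after consent and makes insertion conditional on the vein. Neither section refers to the other's timing. Two sequences fit: consent, scan, allocation, insertion; or consent, allocation, scan, insertion. Only the second lets the judgement depend on the arm.

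**2. Fate of a participant not inserted, or given another device.** Follow-up Assessment visits are timed from insertion, and the last call from line removal, so a patient never inserted has no such schedule. The record review for Doppler examinations covers all subjects, but it cannot find a study-catheter thrombosis where no study catheter was placed. Aim 3 is built on dwell time and functional failure, so that patient contributes nothing. A patient switched to another size can meet the diameter exclusion after allocation.

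**3. Size difference.** If French size is proportional to outer diameter, the ratio is 4.5/4 = 1.125 in diameter and 1.125² = 1.266 in cross-section, about 27% more for Teleflex. This shows that the arms differ in something an inserter could weigh. It is not a threshold.

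**4. The plan's own sample size.** This point does not dispute it. With a one-sided Fisher's exact test, alpha 0.05, power 80% and an 11-point reduction, 13.5% against 2.5% needs 83 per arm, and 83/0.8 gives 104. For 14% against 3% it is 89, and 89 × 1.2 gives 107. Both are close to the stated 106.

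**5. Illustration of possible bias.** The documents supply the BioFlo rate b (12-15%), 106 per arm and the one-sided Fisher test used for planning. Everything else is assumed: no true device effect; a share s = 10-20% of patients with poor veins; r = 2-3 times the thrombosis risk in those veins; and a fraction f = 50-100% of them not inserted in the 4.5 F arm, none in the 4 F arm.

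- Risk in good veins: g = b / (1 − s + s·r). Risk in poor veins: r·g.
- Teleflex rate if the non-inserted are excluded: [(1 − s)g + s(1 − f)r·g] / (1 − s·f), with 106(1 − s·f) patients left.
- Teleflex rate if they are counted as event-free: the same numerator over all 106.

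Mildest case (b = 12%, s = 10%, r = 2, f = 50%): g = 0.12/1.1 = 10.91%, and the numerator is 0.9 × 10.91% + 0.05 × 21.82% = 10.91%. Excluded: 10.91/0.95 = 11.48%, a gap of 0.5 points with 101 patients left. Event-free: a gap of 1.1 points.

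Most severe case (b = 15%, s = 20%, r = 3, f = 100%): g = 0.15/1.4 = 10.71%, and the numerator is 0.8 × 10.71% = 8.57%. Excluded: 10.71%, a gap of 4.3 points with 85 left. Event-free: a gap of 6.4 points.

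| Handling of the non-inserted | Apparent Teleflex advantage (points) | One-sided Fisher rejection rate | Rate with no bias, same arm sizes |
|---|---|---|---|
| Excluded | 0.5 to 4.3 | 4.1% to 16.2% | 3.1% to 3.3% |
| Counted event-free | 1.1 to 6.4 | 5.6% to 35.3% | 3.4% to 3.5% |

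These cases imply 5 to 21 of 106 patients lost from one arm and none from the other. Nothing in the documents says how likely that is.

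**The case against.** The strongest reply is that the concern rests on silence. The bedside evaluation follows directly after consent under a heading that suggests an early step, and allocation belongs to research staff working from a pre-generated list. The scan may well come first in practice. This stands: the documents do not show that allocation comes first. But the list protects the sequence, not a judgement made once the assignment is known, and the plan should settle the order.

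Four stronger readings are tempting and are not supported.

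- *A vein could pass for 4 F and fail for 4.5 F by a size rule.* The plan has no catheter-to-vein ratio, and none of the features the inserter is told to check is a size threshold.
- *Losing one or two high-risk Teleflex patients could halve that arm's rate.* That holds only if those very patients would have clotted. At the planned Teleflex rate of 1-4% (12-15% less 11 points), 106 patients yield 1.1 to 4.2 events. Two patients at an assumed three times the risk carry 0.06 to 0.24 of these, about 6%. Removing them moves 4.0% to (4.24 − 0.24)/104 = 3.85%.
- *Choosing another vein because of the assigned catheter is bias.* It is part of using that device, and a comparison by assigned arm stays valid.
- *The models adjust for a post-allocation vein diameter.* Vein variables are not named as covariates; the plan merely does not rule them out.

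Analysis by assigned arm would indeed reduce the harm, but the plan does not commit to it. It also does not fully cure non-insertion, because the patient has no exposure.

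**Conclusion.** The concern holds as an unclosed route to bias. Vein suitability is not an entry condition, its judgement is not placed before the allocation is known, and no analysis set says what happens to participants not inserted or given another device. Arm-dependent non-insertion or switching, followed by exclusion or by counting as event-free, can bias the thrombosis and catheter-survival comparisons.

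Neither the occurrence nor the size of the bias can be derived from the documents. The ranges in the table rest on assumed shares, risks and losses, with losses in the 4.5 F arm only; the low end is small. If the scan already precedes allocation in practice, the first part of the problem is one of documentation, and the missing analysis set remains. The point is worth a change because the steps needed are already in the plan.

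**What to change.** In Study Design and Initial Assessment, fix the order:

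1. After consent and before the allocation is revealed, perform the planned ultrasound assessment.
2. Record the target vein, its depth and diameter, and the inserter's judgement that it is suitable for either study catheter. Make that judgement an entry condition, without adding a numerical threshold.
3. Only then does the research team open the next allocation.

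In Statistical Analysis, state that everyone allocated is analysed in the assigned arm, and report non-insertions and device switches by arm with reasons. Reword the diameter exclusion so that it cannot remove anyone after allocation. If vein variables enter the adjusted models, use only the measurements taken before allocation.

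The cost is small: existing steps are reordered, the 212 to be randomised is unchanged, and some extra patients are screened. A few patients whose veins suit only the smaller catheter would not be enrolled, which narrows the population slightly. Enrolment was to start in November 2018 and the document is dated 04/30/2019, so recruitment may already be under way. In that case the change applies only to later participants, and its date should be documented.

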travel > 6 hours within past 4 weeks 8. Inflammatory Conditions (IBD, SLE) 9. Immobilization >72 hours 10. Other. Indication for catheter placement will also be recorded: 1. DIVA 2. Antibiotics 3. Incompatible Medications 4. Other

Follow-up Assessment

Investigators will perform a follow-up assessment on all catheters within 24 hours of insertion and then daily for the life of the VAD. Generally all follow-up evaluations will occur between 8 am and 10 am. At each follow-up interval, the researcher will document the time of evaluation and assessment of functionality as well as review the patient chart for signs and symptoms of catheter-related bloodstream infection and document the presence of localized site infection. A catheter is functional if the investigator is able to withdraw 3-5 ml of blood or if the VAD flushes without resistance with 5 mL of saline. Even if the line is actively infusing upon evaluation, the investigator will stop the infusion and assess for functionality by drawing blood and flushing. Data specific to blood sampling will be collected daily. If the catheter was identified to have failed during follow-up assessment the date and time of failure and the reason for failure will be documented. If the catheter failed or was removed prior to the follow-up assessment then the VAD failure time and the assessment of failure and reason for line removal will be obtained through chart review. For all failed catheters, re-insertion attempt data will be tracked through the medical record in the nursing section for venous lines and need for reinsertion of the midline or escalation to a PICC, or CVC will be noted. If the patient is discharged prior to the time of follow-up assessment then the time of discharge will be documented and the VAD will be presumed functional until time of discharge unless otherwise noted in the chart.

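### The daily function check stops any running infusion with no stated exception, and the plan neither excludes nor forbids infusions that may be unsafe to interrupt

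*Combined protocol and SAP*

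**What the plan says.** Follow-up Assessment has every catheter checked within 24 hours of insertion and then daily while it is in place. For a line in use at the check, the rule is: "Even if the line is actively infusing upon evaluation, the investigator will stop the infusion and assess for functionality by drawing blood and flushing". The criterion being tested is: "A catheter is functional if the investigator is able to withdraw 3-5 ml of blood or if the VAD flushes without resistance", using 5 mL of saline. The check supplies the Aim 3 endpoint, for which the Objective section states: "The event is failure of functionality identified during follow-up assessment during hospitalization".

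Study Design sets wide entry criteria: "All inpatients 18 years of age and older that require midline catheter placement by the bedside vascular access team will be eligible participants". Of six exclusions, one concerns a drug: "Are receiving oral, intravenous, or subcutaneous treatment dose anticoagulation (prophylaxis with anticoagulant is permissible". Another removes patients who need multiple lumens. The comparison covers the "functionality of two single lumen midline catheters".

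Initial Assessment lists the reasons for placement: "Indication for catheter placement will also be recorded: 1. DIVA 2. Antibiotics 3. Incompatible Medications 4. Other". Follow-up Assessment has vesicants given through the catheter noted in both groups, with doses counted, and refers to Appendix B for the list.

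**The concern.** The stop is a research procedure imposed on a treatment that is running. The sentence considers the running infusion and settles it by rule. It makes no allowance for the drug, the patient's stability or the treating team's view. With one lumen, a paused drug cannot be moved to another lumen of the same catheter. If the drug were a vasopressor or inotrope, even a short pause might be one that the clinicians would refuse.

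What is at stake is patient safety at the bedside. The Aim 1 endpoint is symptomatic thrombosis confirmed by Doppler and does not depend on this check. For Aim 3, the question is how much ascertainment an exception would cost.

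**Working it through.** **Step 1: does the text limit the rule anywhere?**

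| Where | What it does | Does it limit the stop? |
|---|---|---|
| Study Design, inclusion | Adult inpatients needing a midline from the bedside team | No |
| Study Design, six exclusions | One concerns a drug: treatment-dose anticoagulation | Removes therapeutic intravenous heparin at entry, for example, but no vasoactive drug |
| Study Design, multiple lumens required | Excludes those patients | No; it does not govern what runs through the one lumen |
| Follow-up Assessment, vesicants | Drugs are noted and doses counted | No; recorded, not prohibited |
| Follow-up Assessment, after discharge | Contact by telephone | The stop applies only in hospital |

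Appendix B has 15 red-list entries, of which 6 are vasopressors or inotropes (dobutamine, dopamine, epinephrine, norepinephrine, phenylephrine, vasopressin). Amiodarone is among its 11 yellow-list entries. These counts show that the plan names such drugs. They say nothing about how often one would run through a study line.

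**Step 2: what would an exception cost Aim 3?** The plan gives no figure to reproduce here. This step sizes the cost of the fix, not the harm.

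Inputs:
- 212 participants (Sample Size).
- A 10-day median (Sample Size). The plan words it as time in the vein; I assume it is the time to functional failure.
- A constant hazard (assumed).
- A share of participants whose last pre-discharge check is deferred: 1%, 5% or 10% (assumed).
- Every failure in that interval is uncharted (assumed, worst case).

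Chance of failing in a given 24 hours = 1 − 2^(−1/median):
- Median 10 days: 1 − 2^(−1/10) = 0.067.
- Median 5 days: 1 − 2^(−1/5) = 0.129.
- Median 20 days: 1 − 2^(−1/20) = 0.034.

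Missed failures across both arms = 212 × share deferred × daily probability. At a 10-day median:
- 1%: 212 × 0.01 × 0.067 = 0.14.
- 5%: 212 × 0.05 × 0.067 = 0.71.
- 10%: 212 × 0.10 × 0.067 = 1.42.

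At 5% deferred, the result is 0.36 for a 20-day median and 1.37 for a 5-day median.

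For a given share and median, with one deferred check per participant, these are closer to upper bounds than to estimates. They treat all 212 catheters as in place and unfailed at the last check, although some would have failed earlier and the 212 includes a 20% buffer for loss. They also apply the full daily probability to lines that are infusing at the time, which is itself some evidence of patency.

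**Step 3: what happens to a failure behind a deferred check?**
- If the failure is charted, Follow-up Assessment takes its time from the chart, so nothing need be lost.
- If it is uncharted but found at a later check, its date is coarser by about one day per missed daily check.
- If it is uncharted and no check follows before discharge, it is missed, because "the VAD will be presumed functional until time of discharge unless otherwise noted in the chart".

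**The case against.** The strongest objection is that exposure is inferred. The Introduction presents midlines as an alternative to PICCs for peripheral infusions and mentions critical care only for PICCs. The named indications are DIVA, antibiotics and incompatible medications, with a residual category. The plan describes the vesicants of interest as drugs usually given centrally, and counting doses suits intermittent drugs better than continuous ones. Appendix B is ordered by tissue-damage risk, not by whether a drug can be paused. All of this stands. A reader might infer from Appendix B that vasopressors are expected through these catheters, but the documents do not support that: the list records drugs and does not forecast therapy.

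A second objection is that this is a data-collection sentence, meaning only that a running infusion does not excuse skipping the test, and that staff would use judgement or follow local nursing policy. A reader might infer that the plan tells investigators to override the treating team. It does not say so, and unseen local safeguards may exist. Even so, a clinician who declined the stop would depart from the written procedure, and the plan has no recorded value for that check.

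Third, discretionary deferral could harm Aim 3. No blinding is described, so deferral might differ by arm. This also stands, and it belongs among the costs of the change.

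**Conclusion.** The point holds as a cheap improvement for patient safety. The rule is unconditional as written, and nothing in the plan excludes or forbids infusions that may be unsafe to interrupt. Confidence in that reading is high.

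That confidence does not extend to the size of the risk. The documents give neither the frequency of such infusions through these lines nor the length of the pause, and exposure may be rare. It would go too far to call this a demonstrated safety defect, or to say that the study would in practice stop vasoactive infusions.

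The cost of an exception to Aim 3 is small: at most about 0.7 missed failures across both arms at 5% deferral and a 10-day median. That figure is illustrative and rests on a constant hazard, on reading the plan's median as time to failure, and on every such failure going uncharted.

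**What to change.** Amend the Follow-up Assessment sentence so that the investigator first confirms with the treating nurse or team that the infusion can safely be paused, and only then stops it, draws blood and flushes. The order matters: an exception that rests on the team's judgement protects no one unless the team is asked beforehand.

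If the infusion cannot be paused:
- Record the check as infusing, function not assessed. Do not record it as functional, since neither part of the plan's criterion has been tested.
- Do the check at the next safe opportunity, later the same day or before discharge where possible.
- Date a failure from the chart time if it is charted, otherwise from the next completed check.
- Report deferred checks by arm, and how many were the last before discharge.

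The cost is a conditional clause, one recorded value, a dating rule, a by-arm tally and an occasional repeat visit outside the usual 8 to 10 am window. There is no blood-draw result at a deferred check until it is done. Dating is slightly coarser when the chart is silent, and a failure may be missed if the last check before discharge is deferred. Reporting by arm would reveal differential deferral but would not prevent it.

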Some patients may leave the hospital with the midline in place for additional intravenous therapies. If the patient is discharged with the midline, the research team will discuss the infusion plan with the care management team. Patients will also be provided detailed contact information of the Vascular Access Team (standard practice) at the time of hospital discharge in case any questions or complications arise. If the patient develops any concerning signs or symptoms for the venous thromboembolism, the Vascular Access Team will instruct the patient to return to the outpatient clinic for an evaluation with a member of the Vascular Access Team, schedule an urgent appointment with the medical doctor, or check into the Emergency Department for further evaluation. The research team will document imaging results from these encounters. All patients will receive follow-up phone call assessments by the research team. Patient disposition options include: discharge home/residence or to a skilled nursing facility or transfer to another hospital. If the patient is discharged home, infusion and catheter care occurs via home care or at an infusion center. For patients discharged to a skilled nursing facility, catheter care and infusion is managed by nursing staff at these centers. These patients will continue to be followed in the posthospital setting, specifically to assess for the complication of thrombosis. The research staff will follow-up via telephone call with staff managing the infusion within 48-72 hours of discharge and weekly including the last day of therapy to inquire about the VAD site and function of the catheter and document any complications/results to radiographic imaging. Once the rapy is completed and the catheter is removed, the research team will follow up with the patient or designated legally authorized representative/next of kin via phone to inquire about the access site at 30 days post

line removal. All patients will receive the 30 day follow-up phone contact. Patients will specifically be asked if they developed redness, swelling, or pain at the catheter insertion site and had radiographic evaluation for a blood clot or pulmonary embolism. If the patient has a concern, the research team will forward the concern to [name] and [name] for further evaluation per routine.

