SVT and DVT rates will be calculated based on upper extremity proven diagnosis of SVT and/or DVT in symptomatic cases. Researchers will review all study subject records in EPIC, the electronic medical records system, and screen enrolled subject data for all upper extremity venous Doppler examinations. Radiology interpretations will be reviewed for findings consistent with CR-UEVT. This review will occur thirty days post patient discharge. Symptoms and rationale for imaging will be documented. This information will be obtained by reviewing the order/provider documentation in EPIC. If the patient is diagnosed with thrombophlebitis, the location of the thrombus will also be documented.

Infection rate will be tracked using confirmed catheter-related blood stream infection data from the surveillance team within the epidemiology department. The team utilizes the CDC definition of laboratory-confirmed blood-stream infection (LCBSI). See Appendix A for LCBSI definitions and pathway for diagnosis.

The medication administration record will be queried for all medications given through each catheter. Vesicants that are generally given via central line or considered caustic to the vessel will be noted in both groups. Number of doses will be recorded. See Appendix B for full list of non-neoplastic vesicants. We will also collect data on patients that received alteplase for occlusion. We will specifically evaluate the relationship of alteplase use and how it relates to catheter-related thrombosis, catheter-related bloodstream infection, and functionality of catheter.

Sample Size and Statistical Analysis

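### No masking is stated for the steps that find and classify the primary thrombosis outcome, and Doppler use is not compared by arm; masked report review and one descriptive table would be a cheap improvement

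*Combined protocol and SAP*

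**What the plan says.** **Outcome.** Follow-up Assessment states: "SVT and DVT rates will be calculated based on upper extremity proven diagnosis of SVT and/or DVT in symptomatic cases". A clot is therefore counted only if symptoms are reported or noticed, imaging is ordered, and the report is then judged to qualify. No scheduled Doppler for all participants is described.

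**Finding and classifying events.** "Researchers will review all study subject records in EPIC" and screen them for upper extremity Dopplers thirty days after discharge. Then "Radiology interpretations will be reviewed for findings consistent with CR-UEVT". The document gives no criteria for what makes a finding consistent with, or related to, the catheter.

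**Calls.** "All patients will receive follow-up phone call assessments by the research team". At the call 30 days after line removal, "Patients will specifically be asked if they developed redness, swelling, or pain at the catheter insertion site", and whether they had imaging for a clot. "If the patient has a concern, the research team will forward the concern to" two named individuals for further evaluation.

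**Contact with the device.** Under Study Design, research staff allocate the catheters "according to a pre-generated randomized list at a 1:1 ratio in block randomization". Under Initial Assessment, the research team records which device was placed. Under Follow-up Assessment, investigators draw from and flush every line daily.

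**What is recorded and what is analysed.** "Symptoms and rationale for imaging will be documented", from the order and provider notes. The Statistical Analysis text plans no comparison of imaging between arms. Masking and independent adjudication of thrombosis are not mentioned anywhere. Infection, by contrast, is taken from the epidemiology department's surveillance team, which applies CDC definitions.

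**The concern.** The catheters are different branded products, and the people who elicit symptoms, pass them on and classify reports belong to a group that handles the devices. Aim 1 is also directional: it asks whether Arrowg+ard reduces thrombosis, and the sample-size test is one-sided. Knowledge of the device could act at two points:

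- **Ordering:** which patients with arm symptoms are sent for a scan.
- **Classification:** whether a positive report is counted as symptomatic and catheter-related.

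Either could create or hide a difference between arms. Event numbers are small, so a shift of a few events matters. No adjusted model can recover a clot that was never imaged.

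**Working it through.** **Inputs.** From Sample Size: BioFlo incidence 12–15%; one-sided Fisher's exact test, α = 0.05; power 80% for an 11% lower incidence (read as percentage points); 106 per group, including a 20% buffer. The documents give no figure for unequal detection, so the losses below are assumptions.

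**The plan's own figure.** The exact control rate is not stated, so several pairs were tried with exact Fisher power.
- 14% v 3% needs 89 per group; 89 × 1.2 = 107.
- 13.5% v 2.5% needs 83; 83 / 0.8 = 104.

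Both are close to 106, so the stated size is reproducible and is not in dispute. Removing the buffer gives 106 / 1.2 ≈ 88 per arm, which is used as the lower analysed size.

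**Expected events.** With equal true rates, total events = 2 × n × p.
- Lowest: 2 × 88 × 0.12 = 21.1.
- Highest: 2 × 106 × 0.15 = 31.8.

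Under the design alternative the total is n × (p₁ + p₂), which is smaller: 88 × (0.12 + 0.01) = 11.4 to 106 × (0.15 + 0.04) = 20.1. A false claim of benefit presupposes equal rates, so about 21–32 events is the relevant figure, before any detection loss.

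**False-positive rate under unequal detection.** Let X ~ Bin(n, p) be detected BioFlo events and Y ~ Bin(n, p × d) detected Arrowg+ard events. The true rate p is equal, and d is the fraction of Arrowg+ard clots detected relative to BioFlo. Sum P(X = x) P(Y = y) over all pairs with one-sided Fisher P ≤ 0.05 favouring Arrowg+ard:

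| n per arm | p | d = 1 | d = 0.9 | d = 0.8 | d = 0.7 |
|---|---|---|---|---|---|
| 88 | 12% | 3.1% | 5.2% | 8.5% | 13.4% |
| 88 | 15% | 3.2% | 5.8% | 10.0% | 16.5% |
| 106 | 12% | 3.4% | 5.9% | 10.0% | 16.2% |
| 106 | 15% | 3.5% | 6.6% | 11.8% | 19.9% |

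**Sensitivity to single events.** At 88 per arm, 11 v 4 gives one-sided P = 0.051 and 12 v 4 gives P = 0.032. At 106 per arm the values are 0.053 and 0.033.

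**Sensitivity to the test.** The stated Aim 1 analysis is adjusted logistic regression, with significance at P < 0.05 and no sidedness given. If it were two-sided (assumption; unadjusted Wald test), wins for Arrowg+ard would be about 2% with equal detection and about 4–5%, 6–9% and 10–15% at the three losses. Two-sided Fisher for 12 v 4 at 88 per arm is P = 0.064, so that particular reversal does not occur.

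**The case against.** **Doppler proof is a real safeguard.** An event needs a Doppler finding, reviewers work from radiology interpretations, and the reason for imaging comes from order and provider notes. This stands as a limit on classification bias. It does not govern who is scanned, and it leaves open whether a clot counts as catheter-related or symptomatic.

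**Knowledge of the arm is inferred.** The text speaks variously of research staff, investigators, the research team and researchers. It never says that the same people do every step or that reviewers see the arm. This stands. The inference rests on the described roles together with silence on masking.

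**The plan gathers what is needed.** A reader might infer that nothing in the plan could expose unequal imaging. The documents do not support that: all upper extremity Dopplers, symptoms and reasons for imaging are collected, and every patient gets the 30-day call with named symptom questions. Only the comparison by arm is missing.

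**Ordering is downstream of the catheter.** A reader might also infer that a thrombosis difference accompanied by a difference in ordering should be discounted. Imaging follows symptoms, so a catheter that truly causes fewer symptomatic clots also generates fewer Dopplers. Matched differences are expected under a true effect, and the share positive discriminates only partly with so few events.

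**The main route stays open.** Staff who can see the catheter will still influence ordering, and masked report review does not change that. This is correct, and it is why the table is needed as well.

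**Conclusion.** The point holds as a cheap improvement, not as a flaw that invalidates the trial. The documents show that unmasked ascertainment is possible and would go unreported. They do not show that bias would occur, or which arm it would favour; a one-sided sample-size test is not evidence of direction.

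The size is conditional. With equal true rates of 12–15%, 88–106 per arm and the one-sided Fisher test, detecting 10%, 20% or 30% fewer Arrowg+ard clots moves the false-positive rate from 3.1–3.5% to 5.2–6.6%, 8.5–11.8% or 13.4–19.9%. A 10% loss leaves it close to the nominal 5%, so it would be too strong to say that any modest imbalance is enough for a false claim. The detection losses and their direction are assumptions, and the planned regression would give somewhat different values.

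**What to change.** 1. **Follow-up Assessment, classification.** State that an existing researcher classifies Doppler reports and symptom notes from copies with brand and arm removed, and records whether each event is symptomatic and catheter-related before the arm is disclosed.
2. **Follow-up Assessment, calls.** Where feasible, have the 30-day caller use the questions already listed as a fixed script, without seeing the arm.
3. **Statistical Analysis.** Add a descriptive table by arm of Dopplers ordered, reasons for imaging and share positive, to be read alongside the primary result. State that a difference in ordering does not by itself discount a difference in thrombosis.

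**Cost.** A few sentences of procedure, minor clerical redaction (the full record may show the device, so reviewers need prepared extracts), and one table from data the plan already collects. Sample size, visits, eligibility and treatment are unchanged. Bedside ordering stays unmasked: the table can show unequal ordering but cannot remove it. The documents give no staffing figures, so the low cost is a judgement.
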